10.6 Data Management

The investigator or qualified designee is responsible for recording and verifying the accuracy of subject data. By signing this protocol, the investigator acknowledges that his/her electronic signature is the legally binding equivalent of a written signature. By entering his/her electronic signature, the investigator confirms that all recorded data have been verified as accurate.

Detailed information regarding Data Management procedures for this protocol will be provided separately.

10.7 Publications

This trial is intended for publication, even if terminated prematurely. Publication may include any or all of the following: posting of a synopsis online, abstract and/or presentation at a scientific conference, or publication of a full manuscript. The Sponsor will work with the authors to submit a manuscript describing trial results within 12 months after the last data become available, which may take up to several months after the last subject visit in some cases such as vaccine trials. However, manuscript submission timelines may be extended on OTC trials. For trials intended for pediatric-related regulatory filings, the investigator agrees to delay publication of the trial results until the Sponsor notifies the investigator that all relevant regulatory authority decisions on the trial drug have been made with regard to pediatric-related regulatory filings. Merck will post a synopsis of trial results for approved products on www.clinicaltrials.gov by 12 months after the last subject's last visit for the primary outcome, 12 months after the decision to discontinue development, or product marketing (dispensed, administered, delivered or promoted), whichever is later.

These timelines may be extended for products that are not yet marketed, if additional time is needed for analysis, to protect intellectual property, or to comply with confidentiality agreements with other parties. Authors of the primary results manuscript will be provided the complete results from the Clinical Study Report, subject to the confidentiality agreement. When a manuscript is submitted to a biomedical journal, the Sponsor's policy is to also include the protocol and statistical analysis plan to facilitate the peer and editorial review of the manuscript. If the manuscript is subsequently accepted for publication, the Sponsor will allow the journal, if it so desires, to post on its website the key sections of the protocol that are relevant to evaluating the trial, specifically those sections describing the trial objectives and hypotheses, the subject inclusion and exclusion criteria, the trial design and procedures, the efficacy and safety measures, the statistical analysis plan, and any amendments relating to those sections. The Sponsor reserves the right to redact proprietary information.

For multicenter trials, subsequent to the multicenter publication (or after public disclosure of the results online at www.clinicaltrials.gov if a multicenter manuscript is not planned), an investigator and his/her colleagues may publish their data independently. In most cases, publication of individual trial site data does not add value to complete multicenter results, due to statistical concerns. In rare cases, publication of single trial site data prior to the main paper may be of value. Limitations of single trial site observations in a multicenter trial should always be described in such a manuscript.

Authorship credit should be based on 1) substantial contributions to conception and design, or acquisition of data, or analysis and interpretation of data; 2) drafting the article or revising it critically for important intellectual content; and 3) final approval of the version to be published. Authors must meet conditions 1, 2 and 3. Significant contributions to trial execution may also be taken into account to determine authorship, provided that contributions have also been made to all three of the preceding authorship criteria. Although publication planning may begin before conducting the trial, final decisions on authorship and the order of authors' names will be made based on participation and actual contributions to the trial and writing, as discussed above. The first author is responsible for defending the integrity of the data, method(s) of data analysis and the scientific content of the manuscript.

The Sponsor must have the opportunity to review all proposed abstracts, manuscripts or presentations regarding this trial 45 days prior to submission for publication/presentation. Any information identified by the Sponsor as confidential must be deleted prior to submission; this confidentiality does not include efficacy and safety results. Sponsor review can be expedited to meet publication timelines.

12.0 APPENDICES

12.1 Merck Code of Conduct for Clinical Trials

Merck* Code of Conduct for Clinical Trials

I. Introduction

A. Purpose

Merck, through its subsidiaries, conducts clinical trials worldwide to evaluate the safety and effectiveness of our products. As such, we are committed to designing, implementing, conducting, analyzing and reporting these trials in compliance with the highest ethical and scientific standards. Protection of subject safety is the overriding concern in the design of clinical trials. In all cases, Merck clinical trials will be conducted in compliance with local and/or national regulations and in accordance with the ethical principles that have their origin in the Declaration of Helsinki.

B. Scope

Such standards shall be endorsed for all clinical interventional investigations sponsored by Merck irrespective of the party (parties) employed for their execution (e.g., contract research organizations, collaborative research efforts). This Code is not intended to apply to trials which are observational in nature, or which are retrospective. Further, this Code does not apply to investigator-initiated trials which are not under the control of Merck.

II. Scientific Issues

A. Trial Conduct

1. Trial Design

Except for pilot or estimation trials, clinical trial protocols will be hypothesis-driven to assess safety, efficacy and/or pharmacokinetic or pharmacodynamic indices of Merck or comparator products. Alternatively, Merck may conduct outcomes research trials, trials to assess or validate various endpoint measures, or trials to determine subject preferences, etc.

The design (i.e., subject population, duration, statistical power) must be adequate to address the specific purpose of the trial. Research subjects must meet protocol entry criteria to be enrolled in the trial.

2. Site Selection

Merck selects investigative sites based on medical expertise, access to appropriate subjects, adequacy of facilities and staff, previous performance in Merck trials, as well as budgetary considerations. Prior to trial initiation, sites are evaluated by Merck personnel to assess the ability to successfully conduct the trial.

3. Site Monitoring/Scientific Integrity

Trial sites are monitored to assess compliance with the trial protocol and general principles of Good Clinical Practice. Merck reviews clinical data for accuracy, completeness and consistency. Data are verified versus source documentation according to standard operating procedures. Per Merck policies and procedures, if fraud, misconduct or serious GCP-non-Compliance are suspected, the issues are promptly investigated. When necessary, the clinical site will be closed, the responsible regulatory authorities and ethics review committees notified and data disclosed accordingly.

B. Publication and Authorship

To the extent scientifically appropriate, Merck seeks to publish the results of trials it conducts. Some early phase or pilot trials are intended to be hypothesis-generating rather than hypothesis testing. In such cases, publication of results may not be appropriate since the trial may be underpowered and the analyses complicated by statistical issues of multiplicity.

Merck's policy on authorship is consistent with the requirements outlined in the ICH-Good Clinical Practice guidelines. In summary, authorship should reflect significant contribution to the design and conduct of the trial, performance or interpretation of the analysis, and/or writing of the manuscript. All named authors must be able to defend the trial results and conclusions. Merck funding of a trial will be acknowledged in publications.

III. Subject Protection

A. IRB/ERC review

All clinical trials will be reviewed and approved by an independent IRB/ERC before being initiated at each site. Significant changes or revisions to the protocol will be approved by the IRB/ERC prior to implementation, except that changes required urgently to protect subject safety and well-being may be enacted in anticipation of IRB/ERC approval. For each site, the IRB/ERC and Merck will approve the subject informed consent form.

B. Safety

The guiding principle in decision-making in clinical trials is that subject welfare is of primary importance. Potential subjects will be informed of the risks and benefits of, as well as alternatives to, trial participation. At a minimum, trial designs will take into account the local standard of care. Subjects are never denied access to appropriate medical care based on participation in a Merck clinical trial.

All participation in Merck clinical trials is voluntary. Subjects are enrolled only after providing informed consent for participation. Subjects may withdraw from a Merck trial at any time, without any influence on their access to, or receipt of, medical care that may otherwise be available to them.

C. Confidentiality

Merck is committed to safeguarding subject confidentiality, to the greatest extent possible. Unless required by law, only the investigator, Sponsor (or representative) and/or regulatory authorities will have access to confidential medical records that might identify the research subject by name.

D. Genomic Research

Genomic Research will only be conducted in accordance with informed consent and/or as specifically authorized by an Ethics Committee.

IV. Financial Considerations

A. Payments to Investigators

Clinical trials are time- and labor-intensive. It is Merck's policy to compensate investigators (or the sponsoring institution) in a fair manner for the work performed in support of Merck trials. Merck does not pay incentives to enroll subjects in its trials. However, when enrollment is particularly challenging, additional payments may be made to compensate for the time spent in extra recruiting efforts.

Merck does not pay for subject referrals. However, Merck may compensate referring physicians for time spent on chart review to identify potentially eligible subjects.

B. Clinical Research Funding

Informed consent forms will disclose that the trial is sponsored by Merck, and that the investigator or sponsoring institution is being paid or provided a grant for performing the trial. However, the local IRB/ERC may wish to alter the wording of the disclosure statement to be consistent with financial practices at that institution. As noted above, publications resulting from Merck trials will indicate Merck as a source of funding.

C. Funding for Travel and Other Requests

Funding of travel by investigators and support staff (e.g., to scientific meetings, investigator meetings, etc.) will be consistent with local guidelines and practices including, in the U.S., those established by the American Medical Association (AMA).

V. Investigator Commitment

Investigators will be expected to review Merck's Code of Conduct as an appendix to the trial protocol, and in signing the protocol, agree to support these ethical and scientific standards.

* In this document, "Merck" refers to Merck Sharp & Dohme Corp. and Schering Corporation, each of which is a subsidiary of Merck & Co., Inc. Merck is known as MSD outside of the United States and Canada. As warranted by context, Merck also includes affiliates and subsidiaries of Merck & Co., Inc."

68

12.2 Collection and Management of Specimens for Future Biomedical Research

1. Definitions

- a. Biomarker: A biological molecule found in blood, other body fluids, or tissues that is a sign of a normal or abnormal process or of a condition or disease. A biomarker may be used to see how well the body responds to a treatment for a disease or condition.¹
- b. Pharmacogenomics: The investigation of variations of DNA and RNA characteristics as related to drug/vaccine response.²
- c. Pharmacogenetics: A subset of pharmacogenomics, pharmacogenetics is the influence of variations in DNA sequence on drug/vaccine response.²
- d. DNA: Deoxyribonucleic acid.
- e. RNA: Ribonucleic acid.

2. Scope of Future Biomedical Research

The specimens consented and/or collected in this trial as outlined in Section 7.1.3.2 – Future Biomedical Research Samples will be used in various experiments to understand:

- o The biology of how drugs/vaccines work
- o Biomarkers responsible for how a drug/vaccine enters and is removed by the body
- o Other pathways drugs/vaccines may interact with
- o The biology of disease

The specimen(s) may be used for future assay development and/or drug/vaccine development.

It is now well recognized that information obtained from studying and testing clinical specimens offers unique opportunities to enhance our understanding of how individuals respond to drugs/vaccines, enhance our understanding of human disease and ultimately improve public health through development of novel treatments targeted to populations with the greatest need. All specimens will be used by the Sponsor or those working for or with the Sponsor.

3. Summary of Procedures for Future Biomedical Research

a. Subjects for Enrollment

All subjects enrolled in the clinical trial will be considered for enrollment in the Future Biomedical Research sub-trial.

b. Informed Consent

Informed consent for specimens (i.e., DNA, RNA, protein, etc.) will be obtained during screening for protocol enrollment from all subjects or legal guardians, at a trial visit by the investigator or his or her designate. Informed consent for Future Biomedical Research should be presented to the subjects on the visit designated in the trial flow chart. If delayed, present consent at next possible Subject Visit. Consent forms signed by the subject will be kept at the clinical trial site under secure storage for regulatory reasons. A template of each trial site's approved informed consent will be stored in the Sponsor's clinical document repository.

c. eCRF Documentation for Future Biomedical Research Specimens

Documentation of subject consent for Future Biomedical Research will be captured in the electronic Case Report Forms (eCRFs). Any specimens for which such an informed consent cannot be verified will be destroyed.

d. Future Biomedical Research Specimen(s)

Collection of specimens for Future Biomedical Research will be performed as outlined in the trial flow chart. In general, if additional blood specimens are being collected for Future Biomedical Research, these will usually be obtained at a time when the subject is having blood drawn for other trial purposes.

4. Confidential Subject Information for Future Biomedical Research

In order to optimize the research that can be conducted with Future Biomedical Research specimens, it is critical to link subject' clinical information with future test results. In fact little or no research can be conducted without connecting the clinical trial data to the specimen. The clinical data allow specific analyses to be conducted. Knowing subject characteristics like gender, age, medical history and treatment outcomes are critical to understanding clinical context of analytical results.

To maintain privacy of information collected from specimens obtained for Future Biomedical Research, the Sponsor has developed secure policies and procedures. All specimens will be single-coded per ICH E15 guidelines as described below.

At the clinical trial site, unique codes will be placed on the Future Biomedical Research specimens. This code is a random number which does not contain any personally identifying information embedded within it. The link (or key) between subject identifiers and this unique code will be held at the trial site. No personal identifiers will appear on the specimen tube.

5. Biorepository Specimen Usage

Specimens obtained for the Sponsor will be used for analyses using good scientific practices. Analyses utilizing the Future Biomedical Research specimens may be performed by the Sponsor, or an additional third party (e.g., a university investigator) designated by the Sponsor. The investigator conducting the analysis will follow the Sponsor's privacy and confidentiality requirements. Any contracted third party analyses will conform to the specific scope of analysis outlined in this sub-trial. Future Biomedical Research specimens remaining with the third party after specific analysis is performed will be reported to the Sponsor.

6. Withdrawal From Future Biomedical Research

Subjects may withdraw their consent for Future Biomedical Research and ask that their biospecimens not be used for Future Biomedical Research. Subjects may withdraw consent at any time by contacting the principal investigator for the main trial. If medical records for the main trial are still available, the investigator will contact the Sponsor using the designated mailbox ([contact]).

Subsequently, the subject's specimens will be flagged in the biorepository and restricted to main study use only. If specimens were collected from study participants specifically for Future Biomedical Research, these specimens will be removed from the biorepository and destroyed. Documentation will be sent to the investigator confirming withdrawal and/or destruction, if applicable. It is the responsibility of the investigator to inform the subject of completion of the withdrawal and/or destruction, if applicable. Any analyses in progress at the time of request for withdrawal/destruction or already performed prior to the request being received by the Sponsor will continue to be used as part of the overall research trial data and results. No new analyses would be generated after the request is received.

In the event that the medical records for the main trial are no longer available (e.g., if the investigator is no longer required by regulatory authorities to retain the main trial records) or the specimens have been completely anonymized, there will no longer be a link between the subject's personal information and their specimens. In this situation, the request for withdrawal of consent and/or destruction cannot be processed.

7. Retention of Specimens

Future Biomedical Research specimens will be stored in the biorepository for potential analysis for up to 20 years from the end of the main study. Specimens may be stored for longer if a regulatory or governmental authority has active questions that are being answered. In this special circumstance, specimens will be stored until these questions have been adequately addressed.

Specimens from the trial site will be shipped to a central laboratory and then shipped to the Sponsor-designated biorepository. If a central laboratory is not utilized in a particular trial, the trial site will ship directly to the Sponsor-designated biorepository. The specimens will be stored under strict supervision in a limited access facility which operates to assure the integrity of the specimens. Specimens will be destroyed according to Sponsor policies and procedures and this destruction will be documented in the biorepository database.

8. Data Security

Databases containing specimen information and test results are accessible only to the authorized Sponsor representatives and the designated trial administrator research personnel and/or collaborators. Database user authentication is highly secure, and is accomplished using network security policies and practices based on international standards to protect against unauthorized access.

9. Reporting of Future Biomedical Research Data to Subjects

No information obtained from exploratory laboratory studies will be reported to the subject, family, or physicians. Principle reasons not to inform or return results to the subject include: Lack of relevance to subject health, limitations of predictive capability, and concerns regarding misinterpretation.

If important research findings are discovered, the Sponsor may publish results, present results in national meetings, and make results accessible on a public website in order to rapidly report this information to doctors and subjects. Subjects will not be identified by name in any published reports about this study or in any other scientific publication or presentation.

10. Future Biomedical Research Study Population

Every effort will be made to recruit all subjects diagnosed and treated on Sponsor clinical trials for Future Biomedical Research.

11. Risks Versus Benefits of Future Biomedical Research

For future biomedical research, risks to the subject have been minimized. Buccal swab specimens will be collected inside the cheek with no associated venipuncture to obtain the specimen. Therefore, there will not be an additional risk for the subject.

The Sponsor has developed strict security, policies and procedures to address subject data privacy concerns. Data privacy risks are largely limited to rare situations involving possible breach of confidentiality. In this highly unlikely situation there is risk that the information, like all medical information, may be misused.

12. Questions

Any questions related to the future biomedical research should be e-mailed directly to [contact].

13. References

- 1. National Cancer Institute: http://www.cancer.gov/dictionary/?searchTxt=biomarker
- International Conference on Harmonization: DEFINITIONS FOR GENOMIC BIOMARKERS, PHARMACOGENOMICS, PHARMACOGENETICS, GENOMIC DATA AND SAMPLE CODING CATEGORIES - E15; http://www.ich.org/LOB/media/MEDIA3383.pdf
- 3. Industry Pharmacogenomics Working Group. Understanding the Intent, Scope and Public Health Benefits of Exploratory Biomarker Research: A Guide for IRBs/IECs and Investigational Site Staff. Available at http://i-pwg.org/
- 4. Industry Pharmacogenomics Working Group. Pharmacogenomics Informational Brochure for IRBs/IECs and Investigational Site Staff. Available at http://i-pwg.org/

Trial Visit	Visit 1	Visit 2	Visit 3	Visit 4
Blood for immunogenicity testing	3	3	_	—
Expected total (mL)	3	3	_	—

12.3 Approximate Blood Volumes Collected by Trial Visit and by Sample Types

12.4 Scripted Questionnaire to Be Used by Site Personnel to Obtain Serious Adverse Experience and Medically Attended Adverse Event Information

The following script is to be used at the Phone Call at Day 271 (180 days after Dose 2) in order to probe for any serious adverse experiences and medically attended adverse events that were not previously reported by the subject's parent/legally acceptable representative from Visit 4 (Day 133) through Day 271.

It is the responsibility of the Investigator to carefully assess the information and make a determination whether the adverse experience meets one or more criteria for being reported as a serious adverse experience. Serious adverse experiences and medically attended adverse events identified through the interview process should be reported to the Sponsor/Sponsor Representative.

Questionnaire:

Since the last visit,

- 1. Has your child been admitted to a hospital?
- 2. Has your child experienced a life-threatening episode or an important medical event that required attendance in the Emergency Room or a health care provider's office?
- 3. Has your child seen your doctor, nurse, or health care provider for any other reason other than a well-child visit?
- 4. Did your child have any medical conditions before you agreed to participate in the trial that have become worse or have required more frequent visits to a health care provider since the last visit?
- 5. Has your child developed cancer?
- 6. Has your child developed a new medical condition that I am not aware of?

If the answer to any of the questions above is "yes", the interviewer will determine if the event is a serious adverse experience or a medically attended event and if so, will gather all related information and transcribe onto the appropriate eCRFs.

For each serious adverse experience that is identified through the interview process, information from all available sources, including subject/legally acceptable representative report, subject medical records, hospital discharge summary, and death certificate should be sought to provide a complete description of the adverse experience. All pertinent information must be recorded in the database and retained in the subject's file including, but not limited to:

- Serious adverse experience term
- Onset date
- Causality
- Outcome

Product: V210 Protocol/Amendment No.: A03-01

- The seriousness criteria that the adverse experience met:
 - death
 - caused hospitalization or prolonged existing hospitalization
 - persistent or significant disability
 - life-threatening adverse experience
 - cancer
 - due to an overdose
 - congenital anomaly
 - other medical adverse experience
- Hospitalization admission date
- Hospital discharge date
- Concomitant medications/vaccinations or changes in concomitant medications associated with the serious adverse experience
- Concurrent conditions
- Other medical history
- Procedures associated with the serious adverse experience
- Laboratory results

Term	Definition
ACIP	Advisory Committee on Immunization Practices
AE	adverse event or adverse experience (used interchangeably)
ASaT	All Subjects As Treated
CI	confidence interval
CID	component identification number
CSR	clinical study report
DOD	delta optical density
DTaP	Diphtheria, Tetanus, and Acellular Pertussis
DNA	deoxyribonucleic acid
ECI	event of clinical interest
eCRF	electronic case report form
EDC	electronic data capture
EU	European Union
FDA	Food and Drug Administration
FSA	full analysis set
GCP	Good Clinical Practice
GMFR	geometric mean fold rise
GMT	geometric mean titer
gp	glycoprotein
gpELISA	glycoprotein enzyme-linked immunosorbent assay
Hib	Haemophilus influenzae type b
HIV	human immunodeficiency virus
HZ	herpes zoster
IgG	immunoglobulin G
IPV	inactivated poliovirus
IRB	institutional review board
IVRS	interactive voice response system
IWRS	integrated web response system
М М-R ^{тм} II	measles, mumps, and rubella virus vaccine live, Merck

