6.0 TRIAL FLOW CHART

Visit Number:	1	2	3	4	5
	Randomization/	Vaccination 1		Vaccination 2	
Visit Title:	Vaccination 1	Follow-up ^a	Vaccination 2 ^b	Follow-up ^{a,c}	Phone Call ^c
Trial Timing:	Week 1	Week 6	Week 13	Week 19	Month 9
Trial Days:	Day 1	Days 43-57	Days 91-105	Days 133-147	Days 271-285
Administrative Procedures					
Obtain informed consent	Х				
Obtain informed consent for future biomedical research ^d	Х				
Assign screening number	Х				
Distribute subject identification card	Х				
Review inclusion/exclusion criteria	Х				
Review deferment/exclusion criteria (before Vaccination 2)			Х		
Review medical history	Х				
Review concomitant medication and nontrial vaccines	Х	Х	Х	Х	
Assign treatment allocation/randomization using IVRS/IWRS	Х		Х		
Laboratory Procedures/Assessments					
Obtain buccal swabs (DNA) for Future Biomedical Research ^d	Х				
Obtain blood sample for immunogenicity testing ^e	Х	Х			
Clinical Procedures/Assessments					
Take temperature (oral or equivalent) ^f	Х		Х		
Administer VARIVAX [™] (left arm [or left anterolateral thigh]) ^f					
Group 1: VARIVAX [™] PE34 process	Х		Х		
Group 2: VARIVAX [™] (2016 commercial product)					
Administer M-M-R [™] II (right arm [or right anterolateral thigh]) ^f	Х		Х		
Observe subject for anaphylaxis or other allergic reaction (at least 30 minutes)	Х		Х		
Distribute eVRC/review instructions with subject/legally acceptable representative ^g	Х		Х		
Review eVRC reports with legally acceptable representative ^h		Х		Х	
Educate subject/legally acceptable representative on serious adverse events definition	Х	х	х	х	
and reporting	Λ		Λ		
Review adverse events and serious adverse events ⁱ		Х	Х	Х	
Collect eVRC device				Х	
Active assessment (using scripted safety questions) for occurrence of possible serious					Х
adverse events and medically attended adverse events					Λ
a. Visit 2 and Visit 4 should be performed no sooner than 42 days after the previous	vaccination.				

b. The subject would only be permitted to continue with a delayed vaccination if the visit can be performed within the 14-day window.
c. For subjects who will not receive Vaccination 2, all tasks except vaccination and electronic Vaccination Report Card should be completed.

Informed consent for optional future biomedical research samples must be obtained to collect the DNA sample. d.

04SDBR

Visit Number:	1	2	3	4	5
	Randomization/	Vaccination 1		Vaccination 2	

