7.1.2.1.5 Clinical Follow-up

Subjects will be followed for adverse events through 42 days after each vaccination. Specific injection-site reactions will be solicited from Day 1 through Day 5 after vaccination with the trial vaccine (VARIVAXTM PE34 or VARIVAXTM 2016 commercial product) and M-M-RTM II. Daily temperatures will be recorded on an eVRC from Day 1 through Day 42 after vaccination. Regardless of severity or causality, all unsolicited injection-site reactions; and all systemic adverse events, including varicella-, zoster-, measles-, rubella-like rashes and mumps-like symptoms, will be recorded on an eVRC for Day 1 through Day 42 after vaccination. Serious adverse events, including death, will be reported from Day 1 after the first dose of trial vaccine through Day 180 after the second dose of trial vaccine. Medically attended adverse events will be reported from Day 133 through Day 271. During the phone call at Day 271 (Day 180 Postvaccination 2), a scripted questionnaire will be used to determine if any serious adverse events or medically attended adverse events have occurred for each subject since completing the 42-day safety follow-up period Postvaccination 2.

The parent/legally acceptable representative of each subject will record the safety data on the eVRC and return the eVRC to the trial site at Visit 4. Trial personnel will review the eVRC for completeness, accuracy, and clarity. All information will be accurately recorded on the appropriate eCRFs.

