7.1.5.3 Post-trial (Visit 4: Follow-up Visit, and Visit 5: Follow-up Phone Call)

Visit 4 Follow-up Visit: Subjects will be required to return to the clinic 6 to 8 weeks after Vaccination 2.

Visit 5 Follow-up Phone Call: In addition, 6 months after Vaccination 2, a follow-up phone call will be made to determine if any serious adverse events or medically attended adverse events have occurred since Visit 4.

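### The plan gives the medically attended event period more than one start, so up to 14 days before Visit 4 are covered by no scripted or event-specific question

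*Combined protocol and SAP*

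**What the plan says.** All references are to the combined protocol and SAP.

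- **Section 7.1.2.1.5** sets the reporting window: "Medically attended adverse events will be reported from Day 133 through Day 271". It adds that the call is to find serious or medically attended events that "have occurred for each subject since completing the 42-day safety follow-up period Postvaccination 2". Section 4.2.3.2 gives the same Day 133 start.
- **Section 7.1.5.3** has the call ask about events that "have occurred since Visit 4". It places Visit 4 by time since dose 2: "Subjects will be required to return to the clinic 6 to 8 weeks after Vaccination 2".
- **Section 12.4** describes the script as covering events "from Visit 4 (Day 133) through Day 271". The stem read to the parent is "Since the last visit", and question 4 uses the same anchor.
- **Section 6.0 (flow chart)** puts dose 2 on Days 91-105 and Visit 4 on Days 133-147. Its footnote says "Visit 2 and Visit 4 should be performed no sooner than 42 days after the previous" vaccination. A general review of adverse and serious adverse events is marked at Visits 2, 3 and 4. The scripted assessment that names medically attended events is marked at Visit 5 only.
- **Section 7.2** ends the reporting of all adverse events 42 days after each dose of a live vaccine, and the electronic report card (eVRC) runs for the same 42 days. **Section 7.2.2.1** keeps serious events reportable without a break until about 180 days after dose 2.
- **Section 8.6.2** gives the extended safety period as Day 133 [+14 days] to Day 271 [+14 days]. It treats medically attended events there as Tier 2, with a 95% CI for the between-group difference.

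**The concern.** The call is the only contact at which parents are asked specifically about medically attended events. Its starting point therefore decides which days are asked about. The script treats Visit 4 and Day 133 as the same day. They coincide only when Visit 4 falls on the first day of its window.

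When Visit 4 is later, there can be days on which Section 7.1.2.1.5 makes a medically attended event reportable, but on which the eVRC is closed, the duty to report all adverse events has ended, and the script has not yet begun. These are the days of the extended period closest to vaccination. How many of them are covered would depend on when the visit was booked. A site that follows Sections 7.1.5.3 and 12.4 to the letter would not ask about them at the call.

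**Working it through.** **Inputs.** Dose 2 on trial day D, with D from 91 to 105 (Sections 5.2.2 and 6.0). Visit 4 on day V, with V from 133 to 147 (Section 6.0) and V at least D + 42 (flow chart footnote). The day of vaccination is counted as Day 1 of the 42-day period.

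**The plan's own days.** 91 + 42 = 133 and 91 + 180 = 271. Both figures in the script reproduce, but only for dose 2 on Day 91. For dose 2 on Day 105 the same sums give 105 + 42 = 147 and 105 + 180 = 285.

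**End of the 42-day period.** Day 42 after dose 2 is trial day D + 41, so the first day after it is D + 42.

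**Gap.** The days after the 42-day period and before Visit 4 number V − (D + 42).

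| Dose 2 (D) | Day 42 after dose 2 (D + 41) | Visit 4, flow chart | Gap at earliest V | Gap at V = 147 |
|---|---|---|---|---|
| 91 | 132 | 133-147 | 133 − 133 = 0 | 147 − 133 = 14 |
| 98 | 139 | 140-147 | 140 − 140 = 0 | 147 − 140 = 7 |
| 105 | 146 | 147 | 147 − 147 = 0 | 147 − 147 = 0 |

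In the worst case the uncovered days are Days 133 to 146, and no date is out of window.

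**Other reading of the Visit 4 window.** Section 7.1.5.3 allows Visit 4 up to 8 weeks (56 days) after dose 2. The largest gap is then (D + 56) − (D + 42) = 14 days for any D.

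**Share of the period.** 14 / (271 − 133) = 14/138 = 10.1%.

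**What else covers those days.**

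| Source | Covers the gap? |
|---|---|
| eVRC | No, closed after 42 days |
| Reporting of all adverse events | No, ended after 42 days |
| Serious event reporting | Yes, serious events only |
| Adverse event review at Visit 4 | Possibly; no question on medically attended events is named |
| Script at Visit 5 | No, starts at Visit 4 |

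**The case against.** The strongest reply has four parts.

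1. **The child is seen at the end of the gap.** The flow chart requires review of adverse events, and of concomitant medication, at Visit 4. The script is meant for events not already reported, so it follows on from that visit. This stands in part. A reader might infer that events in the gap are never asked about, and the documents do not support that. Serious events also remain reportable throughout. But the general duty to report non-serious events has lapsed by then, and nothing tells the site to ask at Visit 4 about medically attended events.

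2. **It is not settled which start governs.** Section 7.1.5.3 starts at Visit 4, and the [+14 days] in Section 8.6.2 can be read as the actual Visit 4 date. On that reading the script matches the analysis period. This is fair. The defect is a conflict between sections, not a departure from one undisputed rule. Sections 4.2.3.2 and 7.1.2.1.5 still say Day 133 without qualification.

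3. **Double counting is not shown.** With a fixed Day 133 start and dose 2 on Day 105, a reader might infer that Days 133-146 count in both the 42-day period and the extended period. But Section 8.6.2 carries the [+14 days], Visit 4 for that child cannot come before Day 147, and the script asks only from Visit 4. The documents do not support the inference.

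4. **The effect is small.** Under the flow chart, 14 days needs the earliest dose 2 and the latest Visit 4. Both arms follow the same schedule under blinding, so no bias between groups is shown, and Section 8.6.2 calls these intervals descriptive. All of this stands, and it sets the severity.

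**Conclusion.** The point holds as a minor inconsistency. The start of the medically attended event period differs between sections, and the script uses the later start. Between the end of the 42-day period and Visit 4 there are 0 to 14 days, at most about 10% of the period, covered by no scripted or event-specific question. Capture of non-serious medically attended events on those days is not assured; it is not excluded.

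The 14-day maximum rests on counting the vaccination day as Day 1 and on Visit 4 falling anywhere in its permitted window. The documents give neither the expected spread of Visit 4 dates nor a rate of medically attended events, so the number of events at risk cannot be estimated. The only output affected is a descriptive Tier 2 comparison; no primary hypothesis is touched.

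**What to change.** Define one start for the period: the day after Day 42 following dose 2, or the Day 133 date for a child who did not receive dose 2. State it in the same way in Sections 4.2.3.2, 7.1.2.1.5, 7.1.5.3, 8.6.2 and 12.4.

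In the script, replace "Since the last visit" in the stem, and the same anchor in question 4, with that calendar date, pre-filled by the site. The gap is then 0 days for every child. Alternatively, keep the Visit 4 anchor and add a prompt on medically attended events to the adverse event review already held at Visit 4.

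The cost is a change of wording and one pre-filled date, with no extra contact. The downside of the pre-filled date is up to about two weeks' longer recall for some parents.
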